4.6 Assessments for Safety

4.6.1 Hypoglycaemic Events

Hypoglycaemia will be recorded and documented using the dedicated Hypoglycaemia Episode form.

The classification and recording of hypoglycaemia in the trial will conform to the current ADA guidance (3):

- Level 1 hypoglycaemic event (Glucose Alert Value): is defined as a symptomatic or asymptomatic event with a measured plasma glucose concentration <70 mg/dL (<3.9 mmol/L) but ≥ 54 mg/dL (3.0 mmol/L), [equivalent to a glucose concentration of <63 mg/dL and ≥ 49 mg/dL when using whole blood calibrated results]
- Level 2 hypoglycaemic event (Clinically significant hypoglycaemia): is defined as a symptomatic or asymptomatic event with a measured plasma glucose concentration <54 mg/dL (3.0 mmol/L), [equivalent to a glucose concentration of <49 mg/dL when using whole blood calibrated results]

For Level 1 and Level 2 hypoglycaemic events, the Investigator should also assess whether or not the event was accompanied by symptoms of hypoglycaemia (symptomatic or asymptomatic hypoglycaemic event).

- Level 3 hypoglycaemic event (Severe hypoglycaemia): A severe event characterized by altered mental and/or physical status requiring assistance. Subjects had either altered mental status, and could not assist in their own care, or were semiconscious or unconscious, or experienced coma with or without seizures, and the assistance of another person to actively administer carbohydrate, glucagon, or other resuscitative actions. These events may be associated with sufficient hypoglycaemia to induce seizure or coma. Plasma or blood glucose measurements may not be available during such an event, but

Statistical Analysis Plan				
Trial ID	EudraCT-No.	Date	Status / Version-No.	Page
I8B-MC-ITST	2019-003493-13	15 Jul 2020	Final 1.0	24 of 47

neurological recovery attributable to the restoration of plasma glucose to normal is considered sufficient evidence that the event was induced by a low plasma glucose concentration.

Severe hypoglycaemia will be regarded as SAE and should be recorded on AE and SAE forms. The number of episodes and the percentage of exposed subjects having at least one episode will be provided.

4.6.2 Laboratory Safety Parameters

If not otherwise stated the following assessments will be performed at screening as well as during FUP:

Haematology

Haematocrit	Leucocytes
Haemoglobin	Neutrophile granulocytes (total count and relative)
Erythrocytes	Lymphocytes (total count and relative)
Mean corpuscular volume (MCV)	Monocytes (total count and relative)
Mean corpuscular haemoglobin (MCH)	Eosinophile granulocytes (total count and relative)
Mean corpuscular haemoglobin concentration (MCHC)	Basophile granulocytes (total count and relative)
Thrombocytes (platelets)	

Biochemistry

Sodium	Uric acid
Potassium	Total protein
Calcium	Albumin
Chloride	Total bilirubin
Phosphate	Creatine kinase
Creatinine	Alkaline phosphatase
Urea	Gamma-glutamyltransferase (γ -GT)
AST (aspartate aminotransferase, GOT)	Lactic dehydrogenase (LDH)
ALT (alanine aminotransferase, GPT)	
Total cholesterol	High-density lipoprotein (HDL) cholesterol
Low-density lipoprotein (LDL) cholesterol	Triglycerides

Urinalysis

Protein	Leucocytes
Glucose	pH
Erythrocytes	Ketones

4.6.3 Electrocardiograms

A standard 12-lead ECG will be performed. An ECG will be performed at screening and FUP.

ECG parameters (Heart rate, PR, QRS, QT, QTcB) and any abnormality will be recorded and described in the CRF including the Investigator's assessment of clinical significance ('abnormal, not clinically significant' or 'abnormal, clinically significant'). Clinically significant findings at the screening visit will be recorded as concomitant illness.

Statistical Analysis Plan				
Trial ID	EudraCT-No.	Date	Status / Version-No.	Page
I8B-MC-ITST	2019-003493-13	15 Jul 2020	Final 1.0	25 of 47

Mean result (as reported by the ECG device) will be reported as heart rate. Aggregate data will be reported for all intervals. PQ will be reported as PR.

At subsequent visits, any clinically significant deterioration of a pre-existing condition as well as any new clinically significant findings will be recorded as AEs.

4.6.4 Vital Signs

An examination of the following vital signs will be performed at screening, dosing visits (Day -1 and 2) and FUP.

- Diastolic and systolic blood pressure (BP) is measured after at least 5 min rest in a supine position.
- Pulse (beats per min) measured after at least 5 min rest in a supine position
- Body temperature, tympanic (°C).
- Respiratory frequency

In addition to the pre-specified assessments in protocol Section 2, BP and pulse may be assessed at any time during the trial at the discretion of the Investigator.

4.6.5 Physical Examination

An examination of the following body systems will be performed at screening, dosing visits (Day -1 and 2) and FUP:

- Head, ears, eyes, nose, throat (HEENT), incl. thyroid gland
- Heart, lung, chest
- Abdomen
- Skin and mucosae
- Musculoskeletal system
- Nervous system
- Lymph node
- Other findings

At the screening visit, any abnormality will be recorded and described in the CRF including the Investigator's assessment of clinical significance ('abnormal, not clinically significant' or 'abnormal, clinically significant'). Clinically significant findings at the screening visit should be recorded as concomitant illness.

Statistical Analysis Plan				
Trial ID	EudraCT-No.	Date	Status / Version-No.	Page
I8B-MC-ITST	2019-003493-13	15 Jul 2020	Final 1.0	26 of 47

At subsequent visits, any clinically significant deterioration of a pre-existing condition as well as any new clinically significant findings will be recorded as AEs.

4.6.6 Plasma Glucose for Safety

During the trial, plasma glucose levels will be monitored at the trial site by **CCI** Glucose Analyzer for safety. At the discretion of the investigator, additional blood glucose measurements for safety may be made when there is a suspicion of a hypoglycemic or hyperglycemic episode.

4.7 Other Assessments

The following variables will be evaluated:

- Concomitant medication
- Body Weight
- Pregnancy test (dipstick)
- Alcohol breath test
- Amount of carbohydrates at standard liquid meal

A concomitant medication is any medication, other than the IMPs, which is taken during the trial, including screening and follow-up periods. Details of any concomitant medication must be recorded at trial entry (i.e. at screening). Any changes in concomitant medication must be recorded at each visit as they occur. The information collected for each concomitant medication includes (at a minimum) trade name or generic name, indication, start date and stop date or continuation.

For all female participants, a pregnancy test will be performed at the safety laboratory in a urine sample at the screening visit and from a urine sample at the trial site at Day -1 of Visits 2 and 3 and at follow-up.

An alcohol breath test will be performed at screening and Day -1 using an alcohol meter (‰) by standard procedures at the trial site.

The amount of carbohydrates at standard liquid meal will be measured at both dosing visits at Day 1.

Statistical Analysis Plan				
Trial ID	EudraCT-No.	Date	Status / Version-No.	Page
I8B-MC-ITST	2019-003493-13	15 Jul 2020	Final 1.0	27 of 47

5 STATISTICAL METHODOLOGY

5.1 Analysis Sets

The following analysis sets are defined in accordance with the International Council for Harmonisation (ICH)-E9 guidance (1):

Full Analysis Set (FAS)

The full analysis set (FAS) is based on the intention-to-treat principle and includes all subjects who were randomised. Subjects will contribute to the evaluation ‘as randomised’. PK and PD listings (subjects, who are in the FAS, but not in the mFAS will be identified) and the subject disposition and demographic and baseline characteristics will be based on the FAS.

Modified FAS (mFAS)

The modified FAS includes all subjects of the FAS who complete the study according to the sequence/treatment to which they are randomised. Subjects will contribute to the evaluation ‘as randomised’. Primary and secondary statistical analyses of PK and GD parameters will be conducted on the set of subjects who complete all treatment periods with the same dose and meal intake as the PK parameters and GD response are dependent on the insulin dose which is individualized by subject.

Safety Analysis Set (SFAS)

The safety analysis set includes all enrolled subjects that have received IMP at least once (basal rate) - whether or not they fulfilled all protocol requirements. Subjects in the safety set will contribute to the evaluation ‘as treated’. The safety analysis will be based on the safety analysis set.

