6.5 Discontinuation Criteria

A subject has the right to withdraw from the trial at any time for any reason. A subject's trial participation will also be discontinued for the following reasons:

1. At the discretion of the Investigator if judged non-compliant with trial procedures.
2. At the discretion of the Investigator due to safety concerns.
3. Due to a protocol violation, which, in the clinical judgement of the Investigator or after discussion with the Sponsor, may invalidate the trial by interfering with the PK and PD response of IMP.

Clinical Trial Protocol				
Trial ID	EudraCT-No.	Date	Status / Version-No.	Page
I8B-MC-ITST	2019-003493-13	17 Jan 2020	Final 2.0	35 of 74

4. Due to a concurrent illness, which, in the clinical judgement of the Investigator or after discussion with the Sponsor, may invalidate the trial by interfering with the PK and PD response of IMP.
5. Adverse event (AE): Subject reports symptoms, which are considered unacceptable by the Investigator.
6. If a subject experiences severe hypoglycaemia (according to Section 9.4) at any time during the study
7. Pregnancy or intention to become pregnant.
8. Enrollment in any other clinical study involving an investigational product or enrollment in any other type of medical research judged not to be scientifically or medically compatible with this study.
9. Participation in the study needs to be stopped for regulatory or other reasons consistent with applicable laws, regulations, and good clinical practice (GCP).

In case of discontinuation following dosing with one of the IMPs the subject will, if possible, be called in for a complete follow-up visit. The date and reason of discontinuation will be entered into the CRF. Four categories of discontinuation are distinguished:

- a) Withdrawal by subject. The reason stated by the subject for discontinuation should be stated
- b) Protocol-specific discontinuation criterion is met (from list above)
- c) Lost to follow-up: cessation of participation without notice or action by the subject
- d) Trial terminated by Sponsor
- e) Death
- f) Other

The end of trial form will be completed for all prematurely discontinued subjects.

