6.6 Subject Replacement

A total of 24 subjects should complete the trial according to the sample size calculation (see Section 13.1). To account for discontinued subjects (defined as subjects concluding participation, prior to completion of all protocol-required elements after enrollment/randomisation), up to 28 subjects will be randomised. In case of more than 4 discontinued subjects, four additional replacement subjects may be enrolled (maximum total number of enrolled subjects will not exceed 32 subjects). A replacement subject will be assigned to the same treatment sequence as the subject being replaced.

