13.1 Sample Size Calculation

A sample size calculation was performed based on the primary endpoint and an assumption of an SD of the primary endpoint of 78 min (crossover mean square error of ~55). A sample size of 24 subjects who complete the trial is considered to be sufficient to evaluate a difference between the treatments of 32 minutes with a power of 80%. Discontinued subjects may be replaced to ensure that 24 subjects complete the trial. To take account of discontinued subjects, 28 subjects will be enrolled in the trial. A replacement subject will be assigned to the same treatment sequence as the patient being replaced.

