13.2 Selection of Subjects for Analyses

The following analysis sets are defined in accordance with the ICH-E9 (6) guidance:

Full Analysis Set (FAS)

The full analysis set (FAS) is based on the intention-to-treat principle and includes all subjects who were treated with IMP. Subjects will contribute to the evaluation 'as randomized'.

Modified FAS (mFAS)

The modified FAS includes all subjects of the FAS who complete the study according to the sequence/treatment to which they are randomized. Subjects will contribute to the evaluation 'as randomized'. Primary and secondary statistical analyses of PK and GD parameters will be conducted on the set of subjects who complete all treatment periods with the same dose and meal intake **CCI**

Safety Analysis Set

The safety analysis set includes all enrolled subjects, whether or not they fulfilled all protocol requirements. Subjects in the safety set will contribute to the evaluation 'as treated'. The safety analysis will be based on the safety analysis set.

Clinical Trial Protocol				
Trial ID	EudraCT-No.	Date	Status / Version-No.	Page
I8B-MC-ITST	2019-003493-13	17 Jan 2020	Final 2.0	62 of 74

Before data are released for statistical analysis, a blinded review of all data will take place to identify protocol deviations that may potentially affect the results. This review will be performed without revealing which IMP the subjects are assigned to. The blinding of the IMPs will be maintained for everyone involved in allocating subjects to the analysis sets until data are released for statistical analysis. Obviously erroneous data points may be excluded from the analyses or re-analysed (in case of e.g. serum concentrations). The decision to re-analyse or exclude data points from the statistical analysis is the joint responsibility of the Sponsor, the Principal Investigator and the Trial Statistician.

The subjects or observations to be excluded and the reason for their exclusion will be documented and signed by those responsible prior to database lock. The documentation will be stored together with the remaining trial documentation. The subjects and observations excluded from analysis sets, and the reason for this, will be described in the clinical study report.

Subjects withdrawn from the trial will be listed including the primary reason for withdrawal.

If deemed necessary further endpoints and/or analyses may be added to the SAP. Only analyses not specified in the SAP will be considered as post-hoc analyses.

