3.3 Planned Number of Participants

Up to 28 subjects will be randomised in this trial to ensure that at least approximately 24 subjects complete both the periods to enable evaluation of the primary objective.

A sample size calculation was performed based on the primary endpoint and an assumption of an SD of the primary endpoint of 78 min (crossover mean square error of ~55). A sample size of 24 subjects who complete the trial is considered to be sufficient to evaluate a difference between the treatments of 32 minutes with a power of 80%. Discontinued subjects may be replaced to ensure that 24 subjects complete the trial. To take account of discontinued subjects, 28 subjects will be randomised in the trial. A replacement subject will be assigned to the same treatment sequence as the subject being replaced.

Subject Replacement:

To account for discontinued subjects (defined as subjects concluding participation, prior to completion of all protocol-required elements after enrollment/ randomisation), up to 28 subjects will be randomised. In case of more than 4 discontinued subjects, four additional replacement subjects may be enrolled (maximum total number of enrolled subjects will not exceed 32 subjects). A replacement subject will be assigned to the same treatment sequence as the subject being replaced.

Screening Failures:

Screened subjects who do not meet or comply with all inclusion and exclusion criteria are excluded (screening failures), and their data will be recorded on a screening failure form. The reason for exclusion must be recorded on the screening failure form. Re-screening of screening failures is generally not allowed.

Planned number of sites:

One site in Germany:

- Profil Institut für Stoffwechselforschung GmbH in Neuss

Statistical Analysis Plan				
Trial ID	EudraCT-No.	Date	Status / Version-No.	Page
I8B-MC-ITST	2019-003493-13	15 Jul 2020	Final 1.0	16 of 47

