5.5.2 Presentation of Hypothesis Tests

Mixed effect models will be performed between LY900014 and Humalog[®] using SAS procedure PROC MIXED. Least square means (LS-means), LS-mean differences or ratios, corresponding confidence intervals (CIs) and p-values will be presented.

Unless otherwise noted, all tests of treatment effects will be conducted at a 2-sided alpha level of 0.05, and CIs will be calculated at 95%, 2-sided.

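### Completion is required for the primary analysis of both days, so a subject who leaves after the Visit 3 Day 1 test loses an already observed Day 1 pair

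*SAP*

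**What the plan says.** The mFAS carries the primary and secondary PK and GD analyses. SAP 5.1 defines it by study completion: "The modified FAS includes all subjects of the FAS who complete the study according to the sequence/treatment to which they are randomised". Protocol 13.2 has the same sentence, and the protocol synopsis applies the same condition to the primary analysis. Later in the same paragraph, both documents say these analyses use subjects who finish all treatment periods with the same dose and meal intake. SAP 3.1 and 3.3 likewise link the primary objective to completing both periods. SAP 5.14 tabulates completers without defining them.

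Protocol 6.6 does define discontinued subjects: "defined as subjects concluding participation, prior to completion of all protocol-required elements after enrollment/randomisation". Protocol 6.5 lists reasons for which participation will be discontinued, among them "If a subject experiences severe hypoglycaemia (according to Section 9.4) at any time during the study". Section 9.4 makes severe hypoglycaemia a Level 3 event, defined by altered status needing assistance and not by a glucose value.

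The primary comparison is made separately for Day 1 and Day 2 (protocol 13.4.1, SAP 5.7). The rescue-insulin exclusion in SAP 5.7 removes a subject only for the affected day. The FAS supports listings, individual profiles, disposition and baseline tables (SAP 5.1, 5.5.1). SAP 5.2 allows a sensitivity analysis of exclusions but does not require or specify one.

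**The concern.** The completion condition spans the whole study, while the analysis is per day. What happens after the Visit 3 Day 1 test has no bearing on the Day 1 values, yet it decides whether they are used. The reason given in SAP 5.1 is that PK and GD response depend on the individual insulin dose. That supports matching doses and meals; it does not support requiring completion.

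Two things are at stake. Valid within-subject pairs are lost from a trial planned on 24 of them. Where the cause is a Level 3 event after the bolus, the loss is also related to the response being measured. Because the two wordings conflict, some cases are left to interpretation. SAP 5.7 has the sponsor identify the excluded subjects, and protocol 5.3 says the sponsor's study team is unblinded. That is a reason to settle the rule in text.

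**Working it through.** **1. The plan's own figure.** Inputs: "an assumption of an SD of the primary endpoint of 78 min (crossover mean square error of ~55" (SAP 3.3); 32 min, 80% power and 24 completers (SAP 3.3, protocol 13.1); two-sided alpha 0.05 (SAP 5.5.2). Since 78/√2 = 55.15, the 55 reads as the root mean square error and 78 as the SD of the paired difference. Then SE = 78/√24 = 15.92 min and 32/15.92 = 2.01. Power from the noncentral t with 22 df is 48.5% (normal approximation 52.0%), so the stated 80% is not reproduced. Taking 55 as the SD of the paired difference gives SE = 55/√24 = 11.23 min and power 77.8% (t) or 81.3% (normal). This discrepancy is a separate matter, and the present point does not depend on it. Both SDs are carried below.

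**2. Order of events within a day.** The endpoint is the time from correction bolus to PG = 140 mg/dL. Glucose falling from above 240 mg/dL must pass 140 before it reaches a hypoglycaemic level. PG is scheduled every 5 minutes while above 140 (protocol Tables 2 and 3). A hypoglycaemic event after the bolus therefore follows the crossing that fixes that day's value.

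**3. The cases against the two wordings.**

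| Case | Primary values observed | Study-completion wording | All-periods wording |
|---|---|---|---|
| Level 3 event at Visit 2 | one period only | out, no pair to lose | out, no pair to lose |
| Withdrawal after the Visit 3 Day 1 test | Day 1 pair | out, **pair lost** | out, **pair lost** |
| Level 3 event after the Visit 3 Day 1 bolus | Day 1 pair | out, **pair lost** | out, **pair lost** |
| Level 3 event after the Visit 3 Day 2 bolus | all four | out, read literally | arguably in |
| Only Visit 4 missed | all four | out, read literally with 6.6 | in |
| PG below 54 mg/dL, not Level 3 | as observed | not discontinued on this ground | not discontinued on this ground |

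Rows two and three do not depend on the wording, because Day 2 of period 2 is never done. The last row follows from protocol 8.8.1, which ends the procedure, and 6.5, which does not list such a value as a reason for discontinuation.

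**4. Size.** SE = SD/√n; power for 32 min by noncentral t.

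| Pairs | SE, SD 78 | Power | SE, SD 55 | Power |
|---|---|---|---|---|
| 24 | 15.9 | 48.5% | 11.2 | 77.8% |
| 23 | 16.3 | 46.7% | 11.5 | 75.8% |
| 22 | 16.6 | 44.9% | 11.7 | 73.8% |
| 21 | 17.0 | 43.1% | 12.0 | 71.6% |

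Each unreplaced pair costs about 2 points of power. Removing one of 24 subjects whose difference lies *d* min from the mean moves the mean by *d*/23. The documents give no *d*; for assumed values of 30, 60 and 90 min the shift is 1.3, 2.6 and 3.9 min. At 60 min this is 2.6/15.9 = 0.16 SE.

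**The case against.** The strongest reply is that the sentence governing the analyses is the one on completing all treatment periods, supported by SAP 3.1 and 3.3. On that reading a missed Visit 4 excludes nobody. A subject with a Level 3 event on Visit 3 Day 2 has arguably finished both periods, and protocol 6.5 calls discontinued subjects in for follow-up where possible. This stands: those two cases are an ambiguity and not a certain loss.

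Some stronger readings are tempting, and the documents do not support them:

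- **That subjects with the strongest glucose fall are removed in general.** Only Level 3 events lead to discontinuation. PG below 54 mg/dL ends the procedure only, and frequent sampling and continuous monitoring should keep Level 3 events few.
- **That removals fall on one product.** Leaving the mFAS removes both periods, so each product loses one value. Any bias acts through the within-subject difference, and its size is not known.
- **That people are randomised to replace data already held.** Protocol 6.6 opens the four extra places only after more than 4 discontinuations. If 0–2 Level 3 events and 0–2 missed visits are assumed, the total is at most 4, and 28 − 4 = 24 completers remain.

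The exclusions would also be visible: the data stay in FAS listings and individual profiles, and reasons go in the study report. That helps a reader but does not restore the pair to the primary estimate.

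**Conclusion.** The concern holds for the Day 1 pair of a subject who leaves between the Visit 3 Day 1 test and the end of period 2. That pair is excluded under either wording, and no prespecified analysis brings it back. If the cause is a Level 3 event after the bolus, the exclusion is related to response, and adding other subjects would not undo that selection. For Visit 3 Day 2 events and a missed Visit 4, the finding is that two wordings conflict and one term is undefined. It would be too strong to say that such subjects are excluded.

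The expected effect is small. Losing two pairs raises the SE from 15.9 to 16.6 min, on the assumption that 78 min is the SD of the paired difference. The number of subjects affected is an assumption, since neither document gives a rate for Level 3 events, late withdrawals or missed follow-up visits.

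**What to change.** Replace both completion wordings in the protocol synopsis, protocol 13.2 and SAP 5.1 with one definition per study day, for example:

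*For each study day, the primary analysis set comprises all randomised subjects who received the correction bolus and have a post-bolus PG profile on that day in both periods, regardless of later discontinuation or Visit 4 attendance. The dose, meal and rescue exclusions apply as already specified.*

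Membership should not require PG to have reached 140 mg/dL. An observed-endpoint condition would drop slow responders and so select on the outcome. How a profile that stays above 140 mg/dL to 5 hours enters the model needs its own statement. The set remains one of pairs, so single-period values stay outside it. No change to protocol 6.5 is proposed.

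The cost is wording only: a protocol amendment, or an entry in SAP section 9 as a change from the protocol. The number analysed may differ between Day 1 and Day 2. The separate models already allow for this, but each table should state its own n.
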